- **Aim 2. To develop and establish internal and external validity of a bladder health instrument (BHI) for use in clinical research.**
- **Aim 3. To develop and establish internal and external validity of a bladder health instrument (BHI) for use in a post-partum population.**

Measuring bladder health is central to all future work of the PLUS Research Consortium. As such, a main goal is to create and validate a BHI that is focused on assessing degrees of bladder health among an ethnically and geographically diverse population of community-dwelling women. In part, content validity for the BHI is currently being established based on expert opinion, adaptation of condition specific instruments, incorporation of language from prior PLUS studies involving focus groups and cognitive evaluation. The proposed research will extend this internal validation of the BHI by evaluating dimensional validity of the BHI. A further goal is to establish an external validation with a level of evidence that will allow valid inference to be made based on BHI score in both population based and clinical based research of community-dwelling women and post-partum women. The finalized instrument will be the end product of this study with internal validity (content, construct and dimensional), and external validity (criterion) established for the BHI.

Secondary Aim:

Aim 4. To evaluate the effect of mode of administration (paper and pencil vs. web-based) on item distributions, response rates, and validity.

The BHI is designed to be a self-administered questionnaire (SAQ). At the current time, paper and pencil (PAPI) and web-based/computer assisted self-administered (CASI) instruments are the primary modes the consortium is focusing on for validation of the BHI. There is an accumulation of evidence and knowledge of context based effects associated with mode of survey administration and the design of surveys for mixed-modes.⁴⁻⁷ With rapidly changing technology and increasing availability of online survey administration, the ability to optimally capture data is paramount. While some may prefer the PAPI administration, it is the

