expectation that younger populations of women and adolescent females will prefer and be more apt to utilize the CASI administration. As such, assessment of the BHI in both modes is critical to assess the validity by mode of administration as well as to evaluate survey completion rates based on demographic characteristics. These data will optimize recruitment and survey administration methods for future population based cohort studies.

Some scales have shown that while there are mode effects, the underlying psychometric properties of multi-dimensional scales can remain constant between modes.^{8,9} Other potential biases or sources of error associated with mode of administration are unknown. While a computer mode may increase efficiency of questionnaire completion, it also may produce measurement error; use of a computer may alter the distribution of BHI scores.^{8,9} However, where any change in distribution is found to be constant, this effect can be controlled by score calibration. Therefore, a mode experiment to identify and/or quantify any effect of mode of administration is included in the study protocol.

III. PRELIMINARY DATA

The process of developing and validating a measurement instrument is iterative. Generally, the sequence of tasks for the BHI development is:

1. Development of conceptual model with well specified constructs (or dimensions)
2. Generation of an item pool of new or existing items mapped to constructs
3. Cognitive evaluation of items (face/content validity)
4. Reliability and validity analyses
5. Responsiveness, evaluation of sensitivity to change
6. Establishment of validity in special populations (Spanish fluent and adolescents)

Figure 2 (below) depicts the consortium’s overall plan for development and validation of a bladder health measurement scale (BHS). Steps 1 and 2 have been completed. Step 3 is expected to be completed by May 2019. Step 4, the proposed validation work of this protocol, will commence by June 2019 and be complete by spring 2020. Steps 5 and 6 are planned to be completed through future protocols.

[figure not shown]

Figure 2. Schematic of the overall plan for a bladder health instrument development and validation

III.A. Conceptual framework and item pool

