The material below describes the rationale for the inclusion of each of the sample frames for the BHI validation study as well as recruitment/enrollment approaches for each sample frame. The general population sample will be administered and managed by the SDCC.

IV.B General Population Sample

IV.B.1. Sampling

The BHS is intended for use in the general US population and it is critical that the BHI validation include individuals who meet these criteria. At the current time, the best sampling frame available for the US general population is the US Postal delivery sequence file (DSF); it has been demonstrated to have the smallest amount of coverage error. This is an address based sample frame, which excludes nursing homes and other institutional or long term care facilities. Additionally, it is more efficient and cost-effective than alternative general population sampling methods, such as random digit dialing (RDD). This population will serve as the backbone for the psychometric evaluation; it is the sampling method that best characterizes the general US population.

To ensure the BHI is valid for use in both paper and pencil as well as electronic mode of administration, we plan to randomize participants to a paper and pencil instrument (PAPI) mailed version of the survey or a computer assisted survey instrument (CASI) web-based version of the survey. The sampling plan will include a simple stratification for geography. Using rural urban continuum codes (RUCC) to identify the general urban-to-rural characteristics for every zip code in the United States, we will use a simple 3 level characterization of geography: Urban, Suburban and Rural (including 'moderate city rural'). We will also use this sample frame to evaluate whether a mode effect is present that significantly affects item distribution and whether the psychometric qualities of the BHI are replicable between the two

modes. Sampled households will be randomly assigned to receive a PAPI mailed survey version or a URL for the CASI version.

In addition to the DSF, paradata with listed names of female residents where available, will be used to augment the sample frame.

IV.B.2. Recruitment & Enrollment

Briefly, the following global inclusion and exclusion criteria will determine eligible participants for the general population sample of VIEW:

Inclusion criteria:

- Community dwelling
- Age ≥ 18 years old
- Female sex assigned at birth
- Fluent in written and spoken English

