Households randomly assigned to the CASI mode who do provide an email address will be further randomized to the push to web group or to receive an email with a link to the survey (referred to as the direct email group). This second randomization will allow a full comparison of respondents who fully elect to respond via electronic mode to those who do not. A total of four follow-up letters with a URL to an electronic version of the survey packet will be mailed to non-respondent households of this push-to-web group at 16 day intervals, and between the 2nd and 3rd letter sent, non-respondents will be mailed a paper version of the survey, for a total of 6 contact points. Respondents who provide an email address and who are randomized to the direct email group will be sent an email that contains a URL link to an electronic version of the survey packet. A total of four follow-up emails with a URL link to an electronic version of the survey packet will be emailed to non-respondents at one-week intervals, also with a paper version of the survey mailed between the 2nd URL and 3rd URL, for a total of 6 contact points.

Response rates are expected to differ from PAPI mode, with an expectation of a 10% overall response rate to the request for CASI completion.¹⁵ With the use of a listed DSF frame, households will be randomized to account for expected differential response rates between paper and electronic completion. Within budget allowances, households assigned to an electronic version that do not complete the survey electronically will then be sent a paper version of the survey.

IV.B.2.c. Data Sharing with NIDDK Repository

For both the PAPI and CASI groups, participants will be randomized 1:1 to the placement/timing of receiving text regarding data sharing with NIDDK repository. One group will receive the text immediately at the end of the BHI and the other group will receive the text separately after all study surveys are completed.

[figure not shown]

Figure 4a Stage 1 General Population Sample Plan

Stage 2
Retest and Bladder Diary

[figure not shown]

Figure 4b Stage 2 General Population Retest and Diary Sample Plan

IV.B.3. Retest and 2- day Bladder

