letters, flyers, word of mouth, contacting women interested in prior Consortium studies SHARE and CLEAR, but who were not able to participate, university/institutional websites, institutional research centers/recruiters, social media, community partners & advocates, local community centers, flyers at community events, Craigs List, Facebook

Symptomatic Participants: direct recruitment (screening schedules) from clinical offices (Int med, family med, geriatrics, GYN/Urogyn, urology), flyers in clinical offices, institutional/clinical databases, university/institutional websites, letters, flyers, word of mouth targeting women with bladder symptoms.

Once participants are recruited and enrolled, only those who provide contact information for both home address *and* email will be eligible for randomization to PAPI vs. CASI survey administration. As participants are enrolled, they will be assigned (via block randomization by the SDCC) to either a PAPI or a CASI based mode of the BHI survey. Those who do not have email capability will be included in the PAPI arm.

Participants assigned to PAPI mode will be mailed the survey packet from the SDCC with a brief description of the components of the study, the BHI and criterion questionnaires. The survey packet will include a postage-paid return

envelope addressed to the SDCC. All materials sent to participants will contain logos and contact information for the local site personnel and the PLUS consortium labeling. participants assigned to the electronic version will be emailed a unique link to online BHI completion, and contact information for the local site personnel will be available online for any questions. If the first BHI initial survey is not received by the SDCC within 15 days of mailing or one week of emailing, the PLUS site's research coordinator will contact the participant to remind her to complete the BHI initial survey and criterion questionnaires.

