To the extent that a computer may increase respondent control or increase efficient use of completion time, this may produce some measurement error, but not threaten measurement validity. But if use of a computer (or a paper scale version) alters the distribution of BHI scores, or either mode is found to be a source of systematic variance in BHI score, validity may be threatened.⁷ Response to each individual items will be compared between PAPI and CASI for mode differences. Bland-Altman plots and analysis will be used to compare mean differences using limits of agreement for 95% confidence intervals of items across PAPI and CASI mode. Items that do not fall within LoA will be flagged as being a potential problem for psychometric evaluation. Additionally, psychometric evaluation of dimensions will be done independently for each mode and the final factor structures, including Cronbach alpha, the Kaiser-Guttman rule (Eigenvalues>1.0), factor loading thresholds of 0.60/.40, and scree plots, will be compared. If the structures are the same, then it is assumed that, while mode differences exist for some items, at the aggregate level the internal relationship between items for each factor are consistent. If the structures are not similar, the focus will be on determining if the items that demonstrate significant mode effects do in fact contribute to the structure difference, accomplished by evaluating the factor structures when these items are removed, using the same threshold criteria list above. The goal is to have a single instrument that is capable or working in either PAPI or CASI, recognizing the possibility that measurement differences between modes could result in sub-scales containing different items for each mode. A comparison of responses by mode: PAPI and CASI, will be made both between and within responses from the general population sample and the clinical sample and will also include comparison of item missing values.

IV.E.2.c. External Criterion Validity

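### The PAPI-versus-CASI comparison as written keeps non-randomised women without email in the clinical and postpartum PAPI arms, and has no rule for CASI-assigned paper returns in the general population sample

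*Protocol*

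**What the plan says.** The secondary aim (Protocol Section II, Aim 4) is "To evaluate the effect of mode of administration (paper and pencil vs. web-based) on item distributions, response rates, and validity". The same section presents the comparison as experimental: "a mode experiment to identify and/or quantify any effect of mode of administration is included in the study protocol".

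**Clinical evaluation sample.** Under Section IV.C.2.a, only women giving both a home address and an email "will be eligible for randomization to PAPI vs. CASI survey administration". The paragraph then adds: "Those who do not have email capability will be included in the PAPI arm". Section IV.C.2.b says that mode assignment of postpartum women follows a similar procedure.

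**General population sample.** Section IV.B.1 states: "Sampled households will be randomly assigned to receive a PAPI mailed survey version or a URL for the CASI version". Section IV.B.2.b then adds paper to the CASI arm. In the push-to-web group, "between the 2nd and 3rd letter sent, non-respondents will be mailed a paper version of the survey"; the direct-email group also gets a paper survey between its second and third links. The end of that section describes paper for electronic non-completers again, this time subject to budget. The two statements are not reconciled.

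**Analysis.** Section IV.E.2.b compares items, missing values and factor structure by mode in both samples: "A comparison of responses by mode: PAPI and CASI, will be made both between and within responses from the general population sample", and likewise in the clinical sample. It does not limit the clinical comparison to randomised women. It does not say whether a paper return from a CASI-assigned household counts as PAPI or CASI.

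**The concern.** Randomising mode is what allows a difference between PAPI and CASI responses to be read as an effect of mode. Two separate features weaken that, each in a different sample.

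In the clinical and postpartum samples, women without email can only be in PAPI. If they differ from women with email in age, socioeconomic status or bladder health, the arms differ for reasons unrelated to the questionnaire. Section II itself expects younger women to favour the electronic version, so this is not remote.

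In the general population sample, the CASI arm will contain paper returns. Analysed by assigned mode, these pull the CASI arm towards PAPI and shrink a true item-level effect. Analysed by completed mode, women who ignored the web requests and answered on paper move into the PAPI group by their own choice.

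The results have uses. Section II allows a constant mode shift to be removed by calibrating scores. Section IV.E.2.b flags items on mode differences, re-examines factor structures without them and accepts that sub-scales might differ in content between modes. A selection artefact could therefore be treated as measurement error.

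**Working it through.** **The plan's own figure.** Section IV.B.2.a expects 333 PAPI completes from 1500 households, with response of 10%, 7%, 5% and 3% to successive mailings; Section IV.B.2 gives 3% bad addresses.
- 1500 x 0.97 = 1455 households.
- 1 - 0.90 x 0.93 x 0.95 x 0.97 = 0.2287.
- 1455 x 0.2287 = 332.8, so 333 reproduces, with each rate applied to the remaining non-respondents. The same convention is used for the CASI arm below.

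**Clinical sample.** Section IV.E.3 plans 354 women, 177 per mode. The share without email, q, is not given, and 1:1 randomisation is assumed.
- PAPI = 354(1-q)/2 + 354q; CASI = 354(1-q)/2.
- Non-randomised share of PAPI, s = 354q / PAPI.
- Spurious mode effect = s x D, where D is the assumed difference in SD units between women without and with email.
- Power is for a true 0.3 SD mode effect in randomised women only (two-sided 0.05; effect and alpha assumed).

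| q | PAPI / CASI | s | D = 0.3 | D = 0.5 | Randomised women | Power |
|---|---|---|---|---|---|---|
| 0 | 177 / 177 | 0 | 0 | 0 | 354 | 0.81 |
| 5% | 186 / 168 | 9.5% | 0.03 | 0.05 | 336 | 0.79 |
| 10% | 195 / 159 | 18% | 0.05 | 0.09 | 319 | 0.76 |
| 15% | 204 / 150 | 26% | 0.08 | 0.13 | 301 | 0.74 |
| 20% | 212 / 142 | 33% | 0.10 | 0.17 | 283 | 0.71 |

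With 1:1 randomisation, the planned 177/177 arises only if no woman lacks email. The protocol gives no mode split for the 154 postpartum women; the same formula for s would apply.

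**General population sample.** Section IV.B.2.b expects 10% response to the CASI request, taken here as web response. Let p be the assumed yield of the paper packet among the remaining 90%.
- Paper share of CASI-arm returns, c = 0.90p / (0.10 + 0.90p).
- p = 3%: 0.027 / 0.127 = 21%.
- p = 7%: 0.063 / 0.163 = 39%.

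The 3-7% lies within the per-mailing rates that the protocol expects for paper in the PAPI arm, but it is still an assumption for this arm.

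If CASI-assigned paper completers answer as on paper, a mode effect d becomes d(1-c) when analysed by assignment. With 333 and 361 completes and an assumed d = 0.25 SD, power is 0.91 at c = 0, 0.75 at c = 20%, 0.63 at c = 30% and 0.38 at c = 50%.

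**The case against.** The strongest reply is that nothing irrecoverable has happened. Assigned mode, completed mode and email status can all be known for respondents, and returns are tracked by identifier. Choosing an analysis set is also commonly left to the statistical analysis plan, which is not at hand. This defeats any inference that the randomised contrast is lost. It does not dispose of the clinical point, because the protocol expressly places women without email in the PAPI arm and then describes a comparison that does not set them aside.

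Four further readings might tempt a reader and are not supported.

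- **One arm pair carrying both faults.** Non-randomised women enter PAPI only in the clinical and postpartum samples. Paper fallback is described only in the general population sample.
- **Paper returns counted as CASI.** No section says so. Section IV.B.3 gives the retest in the format the respondent actually used, which if anything suggests labelling by completed format. What can be said is that the rule is absent and each choice has a cost.
- **A confounded direct-email versus push-to-web analysis.** Section IV.B.2.b says "This second randomization will allow a full comparison of respondents who fully elect to respond via electronic mode to those who do not", but Section IV.E plans no such comparison, and a clean contrast exists among women who supplied an email and were randomised again.
- **Unequal response as a design error.** About 23% PAPI against 10% CASI does mean that responders may differ between arms even under assignment. But response rate is itself an Aim 4 outcome, and selection among responders limits any mail-versus-web experiment.

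It is also fair to say that the sizes rest on assumed inputs, that the clinical bias is small at the low end, and that calibration is conditional on a constant shift.

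**Conclusion.** The point holds in two limited parts. In the clinical sample, and similarly in the postpartum sample, the mode comparison as written is not a randomised contrast. Its potential bias is about 0.03-0.13 SD if 5-15% of women lack email and differ by 0.3-0.5 SD, under 1:1 randomisation. In the general population sample, the handling of CASI-assigned paper returns is undefined. They could be about 21-39% of that arm's returns if the paper packet yields 3-7% of remaining non-respondents and the stated 10% is web response.

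The no-email share, the SD differences, the allocation ratio, the paper yield and the effect sizes used for power are assumptions; the protocol gives none of them. Both parts can be put right in the analysis. They affect a secondary aim, so this is a worthwhile correction and not one on which the study's primary conclusions depend.

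**What to change.** Amend Section IV.E.2.b as follows.

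1. **Clinical and postpartum samples:** restrict the PAPI-CASI comparison to women who were randomised to mode. Keep women without email in all other analyses.
2. **General population sample:** make comparison by assigned mode primary. Add a sensitivity analysis by completed mode, adjusted for age, race/ethnicity, socioeconomic status (collected under Section IV.D.2) and the RUCC geography stratum (Section IV.B.1). Report CASI-assigned paper completes as a separate group so that their share and answers are visible.
3. Reconcile the two statements on paper follow-up in Section IV.B.2.b.

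Comparing PAPI-arm paper with CASI-arm web completes should not replace the assigned-mode analysis, because it is itself self-selected.

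The cost is a few sentences and no new data. The clinical mode comparison becomes modestly smaller: at 5-20% without email, 336 to 283 of 354 women remain, and power for an assumed 0.3 SD effect falls from 0.81 to 0.79-0.71. In the general population, the assigned-mode analysis accepts the dilution shown above, and differential response between arms remains a stated limitation.

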While numerous validated condition specific LUTS questionnaires exist for assessing outcomes of LUTS interventions, none fully address the spectrum of bladder health in a non-clinical population. The PLUS consortium reviewed available instruments and assessed each one's ability to assess the bladder functions defined by the PLUS consortium. Validated measures selected to use as external criterion include general health items from the Medical Outcome Study (MOS) to evaluate association with the general bladder related health dimension of general bladder health.²⁰ Naughton et al. determined that the King's Health Questionnaire (KHQ)²¹ and UDI represented Grade A/highly recommended instruments for use in LUTS research.²² The consortium determined that the KHQ and UDI may have insufficient items for evaluation of voiding function, thus the Bristol Female Lower Urinary Tract Symptoms (BFLUTS 3 voiding items (V1-V3))²³ was deemed important to include as an external criterion measure. The PFDI-20²⁴ will also be included as an external criteria with expectations the UDI-6 will strongly correlate with several dimensions of bladder health and the CRADI and POPDI subscales will serve to evaluate discriminate validity.

IV.D.4.a 2-day Bladder Health Symptom Diary

The 2- day Bladder Health Symptom Diary, also based on participant self-report, is an expanded version of a voiding record assessing storage symptoms (frequency, continence, sensation of urge and pain) and emptying symptoms (initiation, flow, efficacy, sensation of urge relief and pain) along with fluid intake and absorbent product usage over two days. This data will be collected from the general population sample, and the clinical evaluation sample.

IV.D.4.b 1-day Bladder Health Frequency Volume Diary

The 1 day Bladder Health Frequency Volume Diary will assess self-measured voiding frequency and volumes along with symptoms of incontinence and absorbent product usage on a one day/24 hour diary. This diary will be mailed from the PLUS research site in a box containing detailed information about the study, a local site map and parking information, a copy of the informed consent, and a 1000 mL voiding hat with instructions for accurate measurement. The Bladder Health Frequency Volume Diary will not be completed by the general population

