Where practically possible, the participant-judge interaction will be scheduled to and actually occur prior to the administration of clinical tests. This is needed to minimize potential for test effects to influence participants interaction with the judge. Further, if the tests are performed before the clinical interview, the results may not be provided to the judge until after they have completed the interview and done the initial 1st and 2nd ratings.

Participants recruited from community or from non LUTS practices who report bothersome symptoms and request evaluation and treatment will be referred for clinical care per the individual PLUS research site's practices. For women recruited from LUTS medical practice/clinic, who were already scheduled for a new patient visit, any additional testing and evaluation beyond the clinical tests outlined above may be performed on the same day as the research appointment and will proceed per the provider's usual clinical practice. Information

gained from routine clinical care may be used in conjunction with clinical data collected for research purposes to inform the expert evaluator's 3rd and 4th rating of bladder health.

IV.E. Analyses

All analyses will be conducted on the general population and the clinical evaluation sample separately, data from the different sources will not be pooled. The final factor structure of the BHI scale will be determined based on the general population data. While the clinical evaluation sample data will not be pooled with the general population data, the clinical evaluation sample data provides a cost-effective means of conducting some external validity tests, i.e., it is not feasible to collect data for frequency/volume diaries or clinical evaluation measures or expert evaluator ratings for the general population sample.

IV.E.1. Distribution evaluation

IV.E.1.a. Ceiling and floor effects

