In PLUS, we are seeking to establish validity to draw a valid inference about a distribution and establish some basic inferential validity. We will operationalize this using a multitrait-multimethod matrix (MTMM) approach¹⁷. For validation of the BHI, each dimension is considered a trait. Method refers to a measurement procedure, which includes consideration of both data source as well as data collection method. The referent data source is the BHI respondent and the referent method is a self-administered survey.

The following are hypothesized dimensions of the PLUS model of bladder health.

- General bladder function (BHI section B)
- Bladder and general day-to-day life (BHI section C)
- Specific Impact: Your bladder and specific activities (BHI section D)
- Psycho-Social: Your bladder and mind (BHI section E)
- Symptom Specific: Bladder performance (BHI section G)

Criterion measures based on respondent self-report that have been identified as expecting to correlate with the dimensions of bladder health are included in Table 2.

Table 2. External Criterion Measures to Evaluate Association with Dimensions of BHI

BHI Section Description	Criterion	Prediction	
		Healthy	Not Healthy
B: General Bladder Health	MOS Global Health	0	X
	MOS Comparative Health	0	X
	MOS Health Transition	0	X
	Section G-LUTS Frequency	X	X
	Section G-Chronicity	X	X
	Section G-Disruption	X	X
	Section G-History	X	X
	KHQ	X	X
	PFDI-UDI	0	X
	BFLUTS V1-V3	0	X
C: Daily Life Impact	MOS Function	0	
	Section G-LUTS Frequency	X	X
	Section G-Chronicity	X	X
	Section G-Disruption	X	X
	Section G-History	X	X
	KHQ	X	x
	PFDI-CRADI, POPDI (discriminant)	0	0
	BFLUTS V1-V3	0	X
D: Specific Activity Impact	MOS Function	0	X

	Section G-LUTS Frequency	X	X
	Section G-Chronicity	X	X
	Section G-Disruption	X	X
	Section G-History	X	X
	BRFSS Physical Activity	X	X
	KHQ	X	X
	Hedonic well-being	X	X
E: Emotional	MOS Emotion	0	X
	Section G: Presence or absence of LUTS		
	Section G-LUTS Frequency	X	X
	Section G-Chronicity	X	X
	Section G-Disruption	X	X
	Section G-History	X	X
	Eudemonic well-being	X	X
Legend 0=not correlated; X=correlated MOS=Medical Outcomes Study; PFDI-20= Pelvic Floor Distress Inventory; BFLUTS=Bristol Lower Urinary Tract Symptoms; KHQ=Kings Health Questionnaire; BRFSS=Behavioral Risk Factor Surveillance Survey (2009)			

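### Table 2 sets the UDI against section B only and CRADI/POPDI against section C only, so for no BHI dimension does it contrast the urinary with the bowel and prolapse subscales

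*Protocol*

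**What the plan says.** Section IV.D.3 gives the PFDI-20 two tasks: "the UDI-6 will strongly correlate with several dimensions of bladder health and the CRADI and POPDI subscales will serve to evaluate discriminate validity". It does not name the dimensions.

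Section IV.E.2.c lists five hypothesised BHI dimensions: sections B, C, D and E, and "Symptom Specific: Bladder performance (BHI section G)". It then introduces Table 2 as containing the "Criterion measures based on respondent self-report that have been identified as expecting to correlate with the dimensions of bladder health". The table has blocks for B, C, D and E, with a separate prediction for healthy and not-healthy women, coded "0=not correlated; X=correlated". The UDI has one row, in block B. The row "PFDI-CRADI, POPDI (discriminant)" appears once, in block C.

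After Table 2, the same section adds the bladder diaries, a 0-10 clinical rating and the clinical tests as further criteria, and describes a matrix that crosses methods with dimensions. It closes by calling positive criteria alone a very low bar and asking that the measure also show absent or negative relationships with other measures.

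Section IV.E says that the general population data determine the final factor structure and that "it is not feasible to collect data for frequency/volume diaries or clinical evaluation measures or expert evaluator ratings for the general population sample".

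**The concern.** The text and the table disagree on the UDI. Beyond that, the layout loses the most informative contrast that the PFDI-20 offers. Its urinary, bowel and prolapse subscales come from the same woman, in the same questionnaire, by the same method. If a BHI dimension correlates more with the urinary subscale than with the other two, shared response style and general pelvic floor distress cannot easily explain it. A UDI correlation seen only for B, and a CRADI/POPDI correlation seen only for C, cannot give that evidence for either.

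At stake is the claim that each dimension reflects bladder problems rather than pelvic floor distress in general. This matters most in the general population sample, which fixes the scale and has no clinical ratings or tests.

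**Working it through.** **Step 1. Count Table 2.** Predictions are written healthy/not healthy; a dash means no row.

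| Criterion | B | C | D | E |
|---|---|---|---|---|
| PFDI-UDI | 0/X | – | – | – |
| PFDI-CRADI, POPDI | – | 0/0 | – | – |
| KHQ | X/X | X/X | X/X | – |
| BFLUTS V1-V3 | 0/X | 0/X | – | – |
| MOS items | three rows, 0/X | 0/blank | 0/X | 0/X |
| Other general measures | – | – | BRFSS activity and hedonic well-being, X/X | eudemonic well-being, X/X |
| BHI section G rows | 4 | 4 | 4 | 5 |
| Rows in block | 10 | 8 | 8 | 7 |

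- UDI: 1 of 4 blocks. CRADI/POPDI: 1 of 4. Both in the same block: 0 of 4.
- Rows predicted 0 in both groups: 1 of 10 + 8 + 8 + 7 = 33, in block C. Blocks B, D and E have none.
- Block E: five of its seven rows are BHI section G items, including "Section G: Presence or absence of LUTS". The other two, MOS Emotion and "Eudemonic well-being", are general measures. None is a bladder instrument from outside the BHI.
- Section G, the fifth hypothesised dimension, has no block, although the UDI and BFLUTS are symptom measures.

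The MOS Function row in C lacks its not-healthy prediction, and the presence-or-absence row in E lacks both. These may be lost in the text at hand, and nothing here rests on them.

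**Step 2. Does the multitrait-multimethod matrix fill the gap?** Its three discriminant criteria in IV.E.2.c compare one BHI dimension with another, within and across methods. In Figure 6 the traits are general bladder health, daily life impact and symptom specific. All concern the bladder. Passing these criteria shows that the dimensions differ from one another. It does not show that any of them follows bladder problems more than bowel or prolapse problems.

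**Step 3. Can the available samples carry the missing contrast?** The protocol gives no correlations, so this is an illustration. Assume that a dimension correlates 0.40 with the UDI-6 (r1) and 0.30 with CRADI or POPDI (r2), and that the two subscales correlate r12 = 0.2 to 0.6. The Williams test for dependent correlations is

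t = (r1 − r2) × √{ (n − 1)(1 + r12) / [ 2·((n − 1)/(n − 3))·|R| + r̄²(1 − r12)³ ] },

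with |R| = 1 − r1² − r2² − r12² + 2·r1·r2·r12 and r̄ = 0.35. Power at one-sided 5% is approximately Φ(t − 1.65).

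For n = 694 and r12 = 0.4: |R| = 1 − 0.16 − 0.09 − 0.16 + 0.096 = 0.686. The denominator is 2 × (693/691) × 0.686 + 0.1225 × 0.216 = 1.402. So t = 0.10 × √(693 × 1.4 / 1.402) = 2.63, and power is Φ(0.98) = 84%.

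| r12 | n = 694: t, power | n = 354: t, power |
|---|---|---|
| 0.2 | 2.29, 74% | 1.63, 49% |
| 0.4 | 2.63, 84% | 1.87, 59% |
| 0.6 | 3.21, 94% | 2.28, 74% |

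Simulation of the same test gives 74% to 95% and 50% to 73%, which agrees to about one percentage point. The implied half-width of a 95% confidence interval for the difference, at r12 = 0.4, is 1.96 × 0.10/2.63 = 0.07 at n = 694 and 1.96 × 0.10/1.87 = 0.10 at n = 354.

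These figures assume complete data and pool healthy with not-healthy women, whereas Table 2 predicts separately for the two. If half of the 694 were not healthy (an assumption; n = 347), power in that group would be about 49% to 73%.

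**The case against.** The strongest reply is that Table 2 is only one part of the external validation. The general population sample also completes the 2-day symptom diary, a bladder measure by another method. The clinical sample adds ratings and tests, and section IV.E presents this division of work as deliberate. Section IV.D.3 does not say how many dimensions CRADI and POPDI should cover, and Table 2 does give them a discriminant row. On this view only one word about the UDI needs correcting, and the added comparisons are analysis detail.

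Much of this stands, and it limits the point. The contradiction is confined to the UDI. The single placement of CRADI/POPDI is a weak design choice and does not conflict with the text, so it would be wrong to say that Table 2 fails both PFDI roles.

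A reader might also infer that section E could be a general mood scale and still meet its predictions, or that nothing ties it to the bladder. The protocol does not support either reading. MOS Emotion is predicted uncorrelated with E in healthy women, a prediction that a mood scale would be expected to fail. The four section G rows on frequency, chronicity, disruption and history are predicted correlated with E in both groups. The diaries, clinical ratings and tests can be applied to E as well.

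The reply does not reach the missing contrast. Diaries, ratings and clinical tests are all bladder measures. They can show convergence, but they cannot show that a dimension is less related to bowel or prolapse distress. In Table 2 only CRADI/POPDI can do that, and for one dimension.

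**Conclusion.** The point holds as a mismatch between text and table with a practical consequence. The UDI appears in one of four blocks where the text expects more than one dimension. No block has the UDI together with CRADI/POPDI. Only block C has a row predicted uncorrelated in both groups, although section IV.E.2.c asks for evidence of that kind. In Table 2, though not in the protocol as a whole, section E has no outside bladder instrument.

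These counts come straight from the table and need no assumption. The power figures do rest on assumed correlations. They show that the contrast is feasible for moderate differences in the full general population sample and less secure in the 354 non-postpartum clinical women or in a not-healthy subgroup. The point does not make the planned validation invalid. It leaves bladder specificity against bowel and prolapse distress untested for B, D and E, and without the urinary comparison for C. It should be corrected before the criteria are applied.

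**What to change.** In Table 2, add UDI-6, CRADI and POPDI rows to each of blocks B to E, with predictions for healthy and not-healthy women, and add a KHQ row to block E. For each dimension, report the difference between its correlation with the UDI-6 and its correlations with CRADI and with POPDI. Give a 95% confidence interval by a method for dependent correlations (Williams or Steiger), overall and in not-healthy women. The general population and clinical samples stay separate, as section IV.E already requires.

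Narrowing the sentence in IV.D.3 to match the present table would remove the contradiction but leave the contrast untested.

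The cost is some table wording and a few more correlations. No new data are needed, because the PFDI-20 and KHQ are already among the chosen criterion measures. The real downside is that a dimension overlapping with general pelvic floor distress may fail the comparison, which is what the comparison is meant to reveal.
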